4.2 Sample Size

Sample size calculation is not applicable, since the study plans to include all eligible breast cancer patients having received neratinib as an extended adjuvant therapy through the EAP in the target European countries. The number of patients is estimated to be up to 200 patients. Using the table below, the precision estimates for a 95% confidence interval (CI) were calculated around proportions ranging from 10% to 50% for a sample size between 150 and 300 patients (see Table 1).

A sample size of 200 patients would allow to assess a category of primary objective (demographic and clinical description of eligible patients) of 10%, 20%, 30%, 40% and 50% of patients with a precision of approximately $\pm 4.1\%$, $\pm 5.5\%$, $\pm 6.4\%$, $\pm 6.8\%$ and $\pm 6.9\%$, respectively.

Based on the feasibility, 120 patients would be enrolled instead of 200 patients originally planned.

A sample size of 120 or 100 patients would allow to assess a category of primary objective (demographic and clinical description of eligible patients) of 10%, 20%, 30%, 40% and 50% of patients with a precision of approximately $\pm 5.4\%$ or 5.9% , $\pm 7.2\%$ or 7.9% , $\pm 8.2\%$ or 9% , $\pm 8.8\%$ or 9.6% and $\pm 9\%$ or 9.8% , respectively.

Table 1 Precision estimates for 95% CI around proportions

Precision estimate*	Proportion				
	10%	20%	30%	40%	50%
Sample size	10%	20%	30%	40%	50%
100 patients	5.9%	7.9%	9%	9.6%	9.8%
120 patients	5.4%	7.2%	8.2%	8.8%	9%
150 patients	4.8%	6.4%	7.3%	7.8%	8.0%
200 patients	4.1%	5.5%	6.4%	6.8%	6.9%
250 patients	3.7%	4.9%	5.7%	6.1%	6.2%
300 patients	3.4%	4.5%	5.2%	5.5%	5.6%

*Precision estimates for a 95% CI were calculated using statistical analysis system (SAS) version 9.4 or higher (SAS Institute, Cary, NC, USA)

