11 PRIMARY OUTCOMES

The primary outcomes will be presented as frequencies and percentages or summary statistics, as appropriate, for the FAS and by subgroups (Section 8.4), subject to pertinence and the number of patients in each subgroup. No statistical testing will be carried out for primary outcomes.

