- Number and percentage of patients by reasons reported for all treatment modifications: Worsening condition, Adverse event, Physician's decision, Patient's wish, Other. All dose changes will be captured in the CRF, therefore a patient can contribute to several reasons. Percentage computed among FAS patients with at least one neratinib treatment modification.
- Number and percentage of patients by reason for first treatment modification: Worsening condition, Adverse event, Physician's decision, Patient's wish, Other. All dose changes will be captured in the CRF, therefore a patient can contribute to several reasons.
- Number and percentage of patients by reason for subsequent treatment modifications⁽¹⁾: Worsening condition, Adverse event, Physician's decision, Patient's wish, Other. All dose changes will be captured in the CRF, therefore a patient can contribute to several reasons.
- Dose at first modification (mg)

- Dose at first modification (mg), category: 40mg, 80mg, 120mg, 160mg, 200mg, 240mg; and <240mg, 240mg, >240mg. Percentage computed among FAS patients with at least one neratinib treatment modification.
- Dose at subsequent modifications (mg)⁽¹⁾
- Dose at subsequent modifications (mg)⁽¹⁾, category: 40mg, 80mg, 120mg, 160mg, 200mg, 240mg; and <240mg, 240mg, >240mg. Percentage computed among FAS patients with the subsequent neratinib treatment modification.

⁽¹⁾Presented individually for each modification.

- Dose reduction at first modification: Yes, No. Percentage calculated among patients with at least one neratinib treatment modification.
 - Dose reduction⁽²⁾
 - Dose reduction⁽²⁾ category: 1 tablet, 2 tablets, > 2 tablets. Percentage calculated among patients with a reduction at first modification.
- Dose escalation at first modification*: Yes, No. Percentage calculated among patients with at least one neratinib treatment modification.
 - Dose escalation⁽²⁾
 - Dose escalation⁽²⁾ category: 1 tablet, 2 tablets, > 2 tablets. Percentage calculated among patients with an escalation at first modification.

⁽²⁾ 1 tablet of neratinib corresponds to 40 mg.

Temporary neratinib treatment discontinuations details:

- Number and percentage of patients with at least one temporary treatment discontinuation. Percentage computed among FAS.
- Number of temporary discontinuations by patient
- Temporary discontinuations per patient category: 1, 2, >2

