- Number and percentage of patients by reason for all temporary discontinuations: Worsening condition, Adverse event, Physician's decision, Patient's wish, Other. All temporary discontinuations will be captured in the CRF, therefore a patient can contribute to several reasons. If the same reason was reported several times for the same patient, the patient contributes only once to the reason. Percentage computed among FAS patients with at least one temporary neratinib treatment discontinuation.
- Number and percentage of patients by reason for first temporary discontinuation: Worsening condition, Adverse event, Physician's decision, Patient's wish, Other. All temporary discontinuations will be captured in the CRF, therefore a patient can contribute to several reasons. Percentage computed among FAS patients with at least one temporary neratinib treatment discontinuation.
- Number and percentage of patients by reason for subsequent temporary discontinuations⁽¹⁾: Worsening condition, Adverse event, Physician's decision, Patient's wish, Other. All temporary discontinuations will be captured in the CRF, therefore a patient can contribute to several reasons. Percentage computed among FAS patients with at least one temporary neratinib treatment discontinuation.
- Dose at first re-initiation (mg)
- Dose at first re-initiation (mg), category: 40mg, 80mg, 120mg, 160mg, 200mg, 240mg; and <240mg, 240mg, >240mg
- Dose at subsequent re-initiations (mg)⁽¹⁾
- Dose at subsequent re-initiations (mg)⁽¹⁾, category: 40mg, 80mg, 120mg, 160mg, 200mg, 240mg; and <240mg, 240mg, >240mg

⁽¹⁾Presented individually for each re-initiation.

- Duration of first treatment interruption (days), calculated as:
 - $(End\ date\ of\ the\ first\ neratinib\ treatment - Start\ date\ of\ first\ re-initiation + 1)$

- Duration of subsequent treatment interruptions (days)⁽²⁾, calculated as:
 - *(End date of the previous neratinib treatment – Start date of subsequent re-initiation + 1)*

⁽²⁾Presented individually for each treatment interruption.

Permanent neratinib treatment discontinuation:

- Number and percentage of patients who discontinued the treatment permanently. Percentage computed among FAS.
- Number and percentage of patients by duration of treatment before discontinuation: ≤ 3 months, > 3 months to < 12 months, 12 months and > 12 months. Percentage computed among FAS patients who discontinued neratinib treatment permanently.

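### Reasons for each later temporary stop of neratinib are divided by all patients with any stop, so the percentages do not give the distribution of reasons at that stop

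*SAP*

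**What the plan says.** SAP section 12.1 has three bullets on reasons for temporary discontinuation, covering all stops, the first stop and subsequent stops. All three end with the same denominator sentence: "Percentage computed among FAS patients with at least one temporary neratinib treatment discontinuation". The third bullet, "Number and percentage of patients by reason for subsequent temporary discontinuations", also carries footnote (1), which reads "Presented individually for each re-initiation". The footnote is worded for re-initiations, but its marker sits on the reasons bullet, so the second, third and later stops are to be shown separately.

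The section also tabulates how many stops each patient had: "Temporary discontinuations per patient category: 1, 2, >2". The plan thus expects some patients to have only one.

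The dose-modification part of the same section works differently. Dose category at the first modification uses patients with any modification. Dose category at subsequent modifications then narrows the base: "Percentage computed among FAS patients with the subsequent neratinib treatment modification". The reasons bullet in that part, "Number and percentage of patients by reason for subsequent treatment modifications", states no denominator. For permanent discontinuation, reasons are taken among patients who discontinued permanently.

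**The concern.** A patient with a single temporary stop has no reason for a second one, yet counts in the denominator for second-stop reasons. A table with one column per stop and one common base mixes two things: how many patients reached that stop, and why they stopped. Adverse events could seem to matter less at each successive stop only because fewer patients have a later stop.

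Reasons for discontinuation are named in the first secondary objective (protocol section 3.2, SAP section 3.2). SAP section 12.1 also asks for these tables by subgroup. If the proportion of interrupters who stop again differs between subgroups, two subgroups with the same distribution of reasons would show different percentages.

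**Working it through.** The plan states no figure for this item, so there is none to reproduce. The check is algebra plus an illustration.

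**Notation.** n1 is the number of FAS patients with any temporary stop, n_k the number with a k-th stop, and x_k the number whose k-th stop was for a given reason.

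**Formulas.**
- SAP rule for subsequent stops: x_k / n1.
- Distribution of reasons at the k-th stop: x_k / n_k.
- Ratio of the first to the second: n_k / n1. This is at most 1, and equals 1 only if every interrupter has a k-th stop.
- With one reason per stop, the x_k add up to n_k across reasons, so the SAP percentages for that stop add up to n_k / n1 instead of 100%.

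**Inputs for the illustration.** SAP section 4.2 says "120 patients would be enrolled instead of 200 patients originally planned"; I use 120 only to set the scale. The rest are assumptions, because the documents give no stop frequencies: half of the 120 have a temporary stop (n1 = 60), 80% of second stops are for an adverse event, and 25%, 50% or 75% of the 60 have a second stop.

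| Patients with second stop (n2) | Of these, for an adverse event (x2) | SAP rule, x2/n1 | Among those with the stop, x2/n2 | SAP column total, n2/n1 |
|---|---|---|---|---|
| 15 | 12 | 12/60 = 20% | 12/15 = 80% | 25% |
| 30 | 24 | 24/60 = 40% | 24/30 = 80% | 50% |
| 45 | 36 | 36/60 = 60% | 36/45 = 80% | 75% |

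**Across successive stops.** Suppose half the patients at each stop go on to another, and 80% of stops are for an adverse event every time.
- First stop: 48/60 = 80%.
- Second stop: 24/60 = 40% under the SAP rule, against 24/30 = 80%.
- Third stop: 12/60 = 20% under the SAP rule, against 12/15 = 80%.

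The fall from 80% to 20% is entirely the falling number of patients with that stop; the reasons do not change.

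**Sensitivity to n1.** If 30% of 120 have a stop (n1 = 36) and n2 is 9, 18 or 27, the adverse-event counts rounded to whole patients are 7, 14 and 22. The SAP rule gives 7/36 = 19.4%, 14/36 = 38.9% and 22/36 = 61.1%. Among those with the stop the figures are 7/9 = 77.8%, 14/18 = 77.8% and 22/27 = 81.5%. The contrast barely moves, because it depends on n2/n1 and not on n1 itself.

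**The case against.** The case for leaving the text alone has four parts.

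- **The quantity has a meaning.** The bullet asks for a percentage of patients, and x_k/n1 is the share of all interrupters who stopped again for that reason. One base across all rows also lets them be compared. This stands, but the SAP does not label the figure that way, and a per-stop table of reasons invites reading it as a distribution.
- **The base can largely be recovered.** Counts accompany the percentages. The table of stops per patient gives n2 (the categories 2 and >2 together) and n3 (>2), so a reader can recompute the second and third stops. This also stands, though not for a fourth or later stop, and it leaves the reader to repair the table.
- **A general rule might apply.** SAP section 8.1 bases percentages on patients with available data, and a patient without a second stop has no reason recorded for it. But the bullet states its own denominator explicitly, and the general rule does not displace it.
- **The output shells are not in these documents**, so the printed layout cannot be checked. That is true, but the shells should follow the SAP text.

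Two stronger readings are tempting, and the documents support neither. A reader might infer that the SAP holds two conflicting rules for reasons. It does not: the narrower base belongs to dose category, and the reasons bullet for subsequent modifications is silent. A reader might also call n_k the patients at risk of a k-th stop. They are the patients who had it; those at risk of a second stop are the ones who restarted after the first, a group closer to n1.

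**Conclusion.** The point holds as a matter of denominator and consistency. As written, the percentages for each later temporary stop equal the within-stop distribution multiplied by n_k/n1. This differs from how the same section handles dose category at subsequent modifications and reasons for permanent discontinuation.

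The size cannot be fixed from the documents. Over the assumed range, with a quarter to three quarters of 60 interrupters stopping again, a true 80% is shown as 20% to 60%. There is no difference if every interrupter has the later stop. The statement about column totals assumes one reason per stop.

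The contrast in the illustration might be read as evidence of bias in the study's findings. It is not: the stop frequencies are invented, the counts are unaffected, and the rows belong to a descriptive secondary table on which no test, sample-size figure or primary outcome depends. The shared sentence is suitable in the bullets for all stops and for the first stop; only the third bullet needs attention. This is a minor correction, worth making because it is simple.

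**What to change.** In SAP section 12.1:

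1. In the bullet on reasons for subsequent temporary discontinuations, compute percentages among FAS patients who had that particular stop (second, third and so on), and print that number with each column.
2. In the bullet on reasons for subsequent treatment modifications, state the matching denominator: FAS patients who had that particular modification.
3. Leave the bullets on all stops and on the first stop as they are.

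If the share of all interrupters who stop again for a given reason is also wanted, it can be shown as a second, labelled percentage.

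The cost is two wording changes in the SAP and, where affected, the table shells. No new data are needed.

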12 SECONDARY OUTCOMES

12.1 Neratinib Treatment Patterns

Neratinib treatment patterns will be described as frequencies and percentages or summary statistics, as appropriate, for FAS and by subgroup EU label; Pathologic stage; Residual disease after neoadjuvant treatment; Risk profile; Previous adjuvant or neoadjuvant therapy and Prior transtuzumab-based regimen overall and last treatment (Section 8.4).

For duration of neratinib treatment calculations, the date of first and last neratinib administration will be taken from the eCRF “Neratinib Treatment” form, variables “Neratinib Initiation date” and “Definitive discontinuation date” respectively. Interruptions, compliance, and dose changes are not considered for duration of neratinib treatment.

Neratinib treatment initiation details:

- Time from breast cancer diagnosis to neratinib initiation (months), calculated as:
 - $(Date\ of\ first\ neratinib\ administration - Date\ of\ diagnosis + 1) / 30.4$
- Time from completion of adjuvant trastuzumab-based therapy to neratinib initiation (months), calculated as:
 - $(Date\ of\ first\ neratinib\ administration - Date\ of\ completion\ of\ adjuvant\ trastuzumab-based\ therapy + 1) / 30.4$
- Performance status scale used at neratinib initiation: ECOG, Karnofsky, Other
 - If ECOG: 0, 1, 2, 3, 4, Unavailable
 - If Karnofsky: 100, 90, 80, 70, 60, 50, 40, 30, 20, 10, Unavailable and 90-100, 70-80, 50-60, 30-40, 10-20, Unavailable
- Performance status computed ECOG score (based on Table 3): 0, 1, 2, 3, 4, Unavailable
- Duration of neratinib treatment (months), calculated as:
 - For discontinued treatment,
 $(Date\ of\ last\ administration - Date\ of\ first\ administration + 1) / 30.4$

Document: ZZA65950_NEAR_SAP_v2.0

Author: [name]

Version Number: 2.0

Version Date: 22SEP2023

- For ongoing treatment, (*EOB date - Start date + 1*)
- Duration of neratinib treatment (categorized): ≤ 3 months, > 3 months to < 12 months, 12 months, >12 months
- Initial daily dosage (mg)
- Initial daily dose (mg), category: 40mg, 80mg, 120mg, 160mg, 200mg, 240mg, ...; and <240mg, 240mg, >240mg

Treatment modifications (dosage changes):

- Number and percentage of patients with at least one neratinib treatment modification. Percentage computed among FAS.
- Number of temporary modifications by patient
- Temporary modifications per patient category: 1, 2, >2. Percentage computed among FAS patients with at least one neratinib treatment modification.

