12.2 Concomitant Treatments

Concomitant treatments will be analyzed over the whole follow-up period. For each therapy type of concomitant treatment [Endocrine therapy, Prophylaxis antidiarrheal and Corrective antidiarrheal therapy in response to AE (diarrhea)], the following variables will be presented for FAS:

- Number and percentage of patients with at least one treatment of the therapy type. Percentage computed among FAS.
- Number and percentage of patients by treatment name. Percentage computed among FAS patients with at least one treatment of the concomitant therapy type.
- Duration of treatment (months)*, calculated as:
 - For discontinued treatments, $(End\ date - Start\ date + 1) / 30.4$
 - For ongoing treatments, $(EOB\ date - Start\ date + 1) / 30.4$

*A patient can contribute with multiple treatments for the same therapy type, the duration of treatment will correspond to the total exposure of the patient to the treatment type.

Note: Other specified treatment names will be coded with WHO Drug version B3 March 2021, the reported and coded terms will be presented in a listing.

For concomitant treatment of Corrective therapy in response to other relevant AE, the following variables will be presented:

- Number and percentage of patients with at least one treatment. Percentage computed among FAS.
- Number and percentage of patients by adverse event description. Percentage computed among FAS patients with at least one corrective therapy in response to other relevant AE.
- Number and percentage of patients by treatment name, as ATC 5th level coded with WHO Drug. Percentage computed among FAS patients with at least one corrective therapy in response to other relevant AE.
- Number and percentage of patients with at least one maximum dosage received. Percentage computed among FAS patients with at least one corrective therapy in response to other relevant AE.
- Duration of treatment (days), calculated as:
 - For discontinued treatments, $(End\ date - Start\ date + 1)$

- For ongoing treatments, (*EOB date - Start date + 1*)

*A patient can contribute with multiple treatments; the duration of treatment will correspond to the total exposure of the patient to the treatment type.

Note: For corrective therapy in response to other relevant AE, the dose, dose unit and frequency, are also collected in the CRF. These details will be presented in a listing.

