13.1 First Recurrence

The patterns of the first recurrence after neratinib initiation will be described based on frequencies and percentages of the following variables for HRAS by EU label and for FAS by Hormone receptor (section 8.4):

- Number and percentage of patients with a first recurrence. Percentage computed among HRAS.
- Number and percentage of patients by type of the recurrence: Invasive ipsilateral breast tumor recurrence (IIBTR), Invasive contralateral breast cancer recurrence (ICBCR), Regional invasive recurrence (RIR), Distant tumor recurrence (DTR) – or metastasis, Second breast cancer.
Percentage computed among HRAS.
 - Number and percentage of patients by site of recurrence. Percentage computed among HRAS with the type of recurrence:
 - IIBTR, ICBCR and RIR: Breast, Chest, Axillary lymph node(s), Skin, Nipple complex, Other
 - DTR or metastasis: Bone, Skin, Non-regional lymph node(s), Lung, Liver, CNS, Pleura, Adrenal glands, Ovary(ies), Left breast, Right breast, Other
 - If second breast cancer, the type: HR+, Triple negative, Other
- Number and percentage of patients with treatment administered for first recurrence
- Number of treatments by patient
- Treatment name: Trastuzumab, Pertuzumab, T-DM1, T-deruxtecan, Lapatinib, Tucatinib, Other
- Treatment duration (months), calculated as:
 - For discontinued treatment, $(End\ date - Start\ date + 1) / 30.4$
 - For ongoing treatment, $(EOB\ date - Start\ date + 1)$

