Appendix 1. Partial Date Conventions

No imputation of missing data will be performed; missing data will not be replaced in this study, unless specified and for the following dates (Table 8). Imputed dates will not be presented in the listings.

Table 8 Missing data imputation rules

Variable	Rule
General rule for partial dates	If the day of event is missing and month and year are available: the day will be imputed to the first day of the month, in case of a start date, and to the last day of the month, in case of an end date. Unless such imputation is illogical. If the day and month are missing, the date will not be imputed.
Date of abstraction	Will not be imputed
Date of informed consent/ non-opposition	Will not be imputed
Date of primary diagnosis of Breast Cancer	General rule for partial dates applies.
Date of pregnancy	Will not be imputed
Start date (Pre-/Post-surgery neoadjuvant therapy)	Will not be imputed.
End date (Pre-/Post-surgery neoadjuvant therapy)	Will not be imputed.
Date of surgery	Will not be imputed.
Date of radiotherapy	Will not be imputed.
Date of weight measurement	General rule for partial dates applies.
Date of performance status assessment (follow-up)	Will not be imputed.
Neratinib initiation date	General rule for partial dates applies.

Variable	Rule
Neratinib definitive discontinuation Date	General rule for partial dates applies.
Treatment modification date	Will not be imputed.
Treatment temporary discontinuation date	Will not be imputed.
Treatment date of re-initiation	Will not be imputed.
Concomitant treatment start date	General rule for partial dates applies.
Concomitant treatment end date	General rule for partial dates applies.
Start date of AE	General rule for partial dates applies.
Date of death	General rule for partial dates applies.
Admission date (Hospitalization due to AE)	Will not be imputed.
Discharge date (Hospitalization due to AE)	Will not be imputed.
Date of recurrence (AE recurrence)	Will not be imputed.
Date of recovery (AE outcome)	Will not be imputed.
Date of first breast cancer recurrence	General rule for partial dates applies.
Treatment start date (Breast cancer recurrence)	General rule for partial dates applies.
Treatment end date (Breast cancer recurrence)	General rule for partial dates applies.
Date of last contact	General rule for partial dates applies.
Date of consent withdrawn	Will not be imputed.

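### SAP 12.1 and 13.1: interruption lengths come out negative, ongoing treatment is left in days under a months heading, and the 12-month class has no stated definition

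*SAP*

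**What the plan says.** **Interruptions (SAP 12.1).** The item headed "Duration of first treatment interruption (days), calculated as" takes the end date of the first treatment period, subtracts the first re-initiation date and adds 1. Later interruptions follow the same pattern: "End date of the previous neratinib treatment – Start date of subsequent re-initiation + 1". Appendix 1 (Table 8) names the recorded item only as "Treatment temporary discontinuation date".

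**Duration in months (SAP 12.1 and 13.1).** Neratinib duration is declared in months. The formula for discontinued treatment divides by 30.4. The one for ongoing treatment stops at "For ongoing treatment, (*EOB date - Start date + 1", with no divisor. Section 13.1 does the same for treatment of the first recurrence, under the heading "Treatment duration (months), calculated as". Section 12.2, for concomitant treatments reported in months, keeps the divisor: "For ongoing treatments, $(EOB\ date - Start\ date + 1) / 30.4".

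**Classes (SAP 12.1).** All patients are grouped as "Duration of neratinib treatment (categorized): ≤ 3 months, > 3 months to < 12 months, 12 months, >12 months". Patients who stopped permanently are grouped "by duration of treatment before discontinuation: ≤ 3 months, > 3 months to < 12 months, 12 months and > 12 months".

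**The concern.** These are derivation rules that a programmer is meant to follow literally. Done that way, every interruption of two or more days between stop and restart has a negative length, and the mean, SD and maximum of treatment duration mix days with months. The third problem is an undefined class rather than a wrong formula. The protocol's Background describes a one-year course, so patients who complete treatment can be expected to cluster at the 12-month boundary. How they split between under, at and over 12 months then depends on a choice the SAP text does not make.

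Treatment duration and temporary discontinuation are named secondary objectives (protocol 3.2, SAP 3.2), and section 12.1 repeats these summaries across several subgroups. Recurrence treatment duration is exploratory.

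**Working it through.** The plan prints no numerical result for these formulas, so there is no figure to reproduce. The check evaluates each formula as written.

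**Inputs.** Index dates run from 01 August 2017 to 31 December 2020 (SAP 7.1); the cut-off is 05 July 2022 (SAP 7.5); the divisor is 30.4 and the classes are those of SAP 12.1. The March dates are an illustration.

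**1. Interruption: end - restart + 1**

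- Restart the next day: -1 + 1 = 0.
- Restart two days later: -2 + 1 = -1.
- End 10 March, restart 24 March: -14 + 1 = -13.

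For that last example, the true time off drug is 24 - 10 - 1 = 13 days if 10 March was the last dosing day, or 24 - 10 = 14 days if it was the first day off drug. Swapping the dates and keeping the +1 gives 15, which is wrong under either reading.

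**2. Ongoing treatment: EOB - start + 1, undivided**

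- Latest index date, 31 December 2020 to 05 July 2022 inclusive: 552 days; 552 / 30.4 = 18.2 months.
- Earliest index date, 01 August 2017 to 05 July 2022 inclusive: 1,800 days; 1,800 / 30.4 = 59.2 months.
- Recurrence treatment, for example 06 April to 05 July 2022: 91 days, entered as 91 months instead of 91 / 30.4 = 2.99.

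Each value is 30.4 times too large. The class limits are 3 x 30.4 = 91.2 days and 12 x 30.4 = 364.8 days, so an ongoing neratinib course is classed as follows:

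| Days on drug at end of observation | Class as written (months) | Correct class (months, unrounded) |
|---|---|---|
| 4 to 11 | > 3 to < 12 | ≤ 3 |
| 12 | 12 | ≤ 3 |
| 13 to 91 | > 12 | ≤ 3 |
| 92 to 364 | > 12 | > 3 to < 12 |
| 365 or more | > 12 | > 12 |

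Anyone still on neratinib at the cut-off has at least 552 days and is in the right class either way. The misclassified patients are those whose observation ended early while they were on drug.

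**3. The 12-month class: days / 30.4 = 12**

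- 364 / 30.4 = 11.97 and 365 / 30.4 = 12.01, so no whole number of days gives 12. Unrounded, the class is empty and a 365-day course falls above 12 months.
- Rounded to one decimal (11.95 up to 12.05): 364 to 366 days.
- Rounded to whole months (11.5 up to 12.5): 350 to 379 days; 380 / 30.4 = 12.5 exactly, a tie.
- Truncated to completed months (12 up to 13): 365 to 395 days.

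The partial-date rule adds to this. A start on 15 January 2019 with a stop known only as January 2020 is imputed to 31 January 2020. That is 382 days, or 12.6 months, which is above 12 under the first three conventions and in the class only under truncation.

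**The case against.** The strongest reply is that the intent is plain and the reach is small.

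- **Interruptions.** SAP 12.1 takes the date of last administration from the definitive discontinuation date. If temporary stops work the same way, the written formula gives exactly minus the days off drug: the size is right and only the sign is wrong. A negative duration would be noticed in the first output. That is fair, but the SAP makes this link for permanent stops only, so the convention for temporary stops is open and a correction has to state it.
- **Ongoing treatment.** The cut-off is at least 552 days after any index date and the described course is one year, so few patients should still be on drug. Patient death is a listed reason for permanent discontinuation, so deaths on treatment need not enter the ongoing formula. The class table for permanent discontinuation covers only patients who stopped, so the missing divisor cannot affect it. The upper figure of 1,800 needs nearly five years of neratinib. All of this stands and limits the effect. It does not make the formula right, and a few values of this size would distort a mean, SD or maximum.
- **12-month class.** SAP section 9 refers to table shells supplied with the SAP. They are not among the documents available here and could hold a rounding rule. Completion is also tabulated directly, through end of the treatment period as a discontinuation reason. This makes the class the weakest of the three parts.

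**Conclusion.** The concern holds. Two of the three parts are formulas that give wrong values as written: negative interruption lengths, and ongoing durations 30.4 times too large. A PDF extraction fault is an unlikely explanation, because each pattern occurs in two places and neighbouring formulas keep the divisor. The third part is a class that is necessarily empty if durations are not rounded, and otherwise covers anything from 3 day counts (364 to 366) to 31 (365 to 395), depending on the convention. That part assumes the table shells do not already settle it.

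The consequence is confined to descriptive secondary and exploratory summaries. The number of patients with ongoing treatment is not given and could be small. The primary outcome is not involved, the formulas for iDFS, DDFS, CNS metastasis and OS all carry the divisor, and no effect on the Kaplan-Meier analyses of treatment is shown. It should be fixed because a silent repair during programming would leave the day convention and the class limits to be chosen after the data have been seen.

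**What to change.** 1. State whether the recorded temporary discontinuation date is the last dosing day or the first day off drug. Replace both interruption formulas with re-initiation date - end date - 1 in the first case, or re-initiation date - stop date in the second.
2. Add / 30.4 to the ongoing-treatment formulas in SAP 12.1 and 13.1, as section 12.2 already does.
3. Define the 12-month class by a pre-specified day window or rounding rule, use it in both class lists of section 12.1, and check that the table shells agree.

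The cost is six lines of SAP text (two interruption formulas, two ongoing-treatment formulas, two class lists) and the matching programming; no new data are needed. Protocol 4.7.1 gives the route: amend the SAP before database lock or, if the database is already locked, report the corrections as deviations in the study report or statistical analysis report.
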